Study Sponsor	Rhizen Pharmaceuticals S.A.
Study Centers	Approximately about 15 study centers
Study Objectives	
Primary Objectives
 
 • To characterize safety, tolerability and to establish the maximum tolerated dose (MTD) of Tenalisib in combination with Romidepsin in patients with R/R T-cell lymphoma. 
Secondary Objectives
 
 • To assess the preliminary anti-tumor activity of various dose levels of Tenalisib in combination with Romidepsin, as determined by the objective response rate (ORR) and Duration of Response (DoR) • To characterize the Pharmacokinetics (PK) of Tenalisib and Romidepsin when given in combination. 
Exploratory Objectives
 
 • To correlate clinical efficacy with markers that include but are not limited to quantitative and qualitative measurements of malignant cells, cytokines, and chemokines in blood/serum.
Endpoints	
Safety:
 
 • Adverse Event (AE), Grade 3/ 4 AEs, Serious and fatal Adverse Event (SAE), graded using NCI CTCAE Version 5.0. 
Efficacy:
 
 • Objective response rate (ORR), defined as sum of CR and PR rates, assessed according to the Lugano Classification for initial evaluation, staging, and response assessment of Hodgkin/non-Hodgkin lymphoma in PTCL patients; and according to the modified Severity Weighted Assessment Tool (mSWAT) in CTCL patients. • Duration of Response (DoR), calculated as time from the initial response to documented disease progression. 
Pharmacokinetics:
 
 • PK Parameters [AUC $(0-\infty)$, AUC $(0-t)$, C_{max}, t_{max}, K_{el}, and $t_{1/2}$] of Tenalisib and Romidepsin.

	
Correlative/Exploratory:
 
 Correlative markers include baseline and on-treatment serum levels of chemokines, cytokines, antibodies to tumor antigens, and other immune mediators (e.g. SIL2R and CTACK for PTCL; CD30, IL-31 and IL-32 for CTCL) as deemed relevant by the sponsor. 																

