3.4.5 Precautions and Risks Associated with Investigational Products

3.4.5.1 Tenalisib

Monitoring of liver enzymes and levels of TSH, T3, and T4 in subjects receiving Tenalisib is recommended based on target organ toxicity. Patients will be monitored for increased ALT/AST, skin rash, neutropenia as these are reported with Tenalisib. In addition, enteritis (colitis), pneumonia/pneumonitis as these events are reported with other PI3K inhibitors.

Tenalisib elicits no photo instability upon exposure to ultraviolet (UV) radiations. However, in absence of in vitro data, possibility of photo-toxicity with Tenalisib cannot be ruled out.

Tenalisib shows inhibition of CYP3A4 enzyme. Therefore, concomitant administration of Tenalisib with predominant CYP3A4 substrates (e.g. calcium channel blockers, warfarin, carbamazepine, macrolide antibiotics, lovastatin, simvastatin, terfenadine) may reduce clearance of these drugs increasing the risk of adverse events. Similarly, as Tenalisib is inhibited by CYP3A4/5 and CYP2C9, there is possibility of drug interaction with inhibitors or inducers of CYP3A4 and CYP2C9. If concomitant treatment of these drugs are clinically warranted, careful observation of the patient is advised. Strong inhibitor or inducers should be avoided as directed in Section on prohibited medication. Please refer to the recent Investigator Brochure for additional safety information.

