6.4 Laboratory Investigations

Laboratory tests for hematology, chemistry and urinalysis are specified in Table 4.

Table 4: Laboratory Tests for Hematology, Chemistry and Urinalysis

Hematology	Chemistry Panel I	Chemistry Panel II	Urinalysis	Other
Hematocrit	Total bilirubin	Blood glucose	Blood	Serum β -hCG
Hemoglobin	Alkaline phosphatase (ALP)	Urea or blood urea nitrogen ^a	Glucose	Urine pregnancy test
CBC with differentials	Alanine aminotransferase (ALT)	Creatinine	Protein	PT/INR
Platelet count	Aspartate aminotransferase (AST)	Albumin	Specific gravity	Serology (Only at Screening) (Hepatitis B, Hepatitis C, HIV, EBV and CMV)
WBC (Total and differentials)	Lactate dehydrogenase (LDH)	Total protein	Microscopic exam ^b	
Red blood cell count	Gamma-glutamyl transferase (GGT)	Total Cholesterol		
Absolute neutrophil count	Sodium	Triglyceride (TG)		
Absolute lymphocyte count	Potassium	LDL		
	Calcium	HDL		
	Phosphorous	TSH		
	Bicarbonate or Carbon dioxide (CO2)	T3 (Total or Free)		
	Chloride	T4 (free)		
	Magnesium			

^a Blood Urea Nitrogen is preferred; if not available Urea may be tested.

^b Microscopic exam, if abnormal results are noted

Blood drawn for these tests will be specified in informed consent form (ICF). The investigations will be performed at each local laboratory. Additional details will be provided in the study-specific Laboratory Manual.

Screening labs will be done within 7 calendar days prior to the initiation of trial treatment. If these initial examinations are obtained within 72 hours of Cycle 1 Day 1, the labs need not be repeated. Re-screening can be done at the discretion of PI. Scans and other investigations

to document measurable disease should be performed ≤ 28 weeks prior to initiation of treatment.

6.5 12-Lead Electrocardiograms

An ECG will be performed at the time points mentioned below table. Additional ECGs will be obtained if clinically indicated. A single ECG will be performed at all-time points unless specified. Triplicate ECGs only need to be performed at other time points to confirm the significant changes of single ECG (e.g. If QTcF > 450 msec on single EKG at screening or > 500 msec during treatment). All ECGs will be performed on local equipment. Window period of ± 5 minutes will be applicable to 30 min time point. For all time 1 hr time points, ± 15 minutes window period will be applicable.

Dose Escalation		
Days	Time points	Note
Screening	Within last 28 days	-

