11.3 Documentation Required to Initiate Trial

Before the trial may begin, documentation required by the health authorities will be provided by the Sponsor. Documents at a minimum required to begin a trial include, but are not limited to: a signature-authorized protocol and contract; a copy of the official IRB/IEC approval of the trial and the IRB/IEC members list; current Curricula Vita for the principal investigator and any associate investigator(s) who will be involved in the trial; indication of appropriate accreditation for any laboratories to be used in the trial and a copy of the normal ranges for tests to be performed by that laboratory; appropriately completed and signed Form FDA 1572 (Statement of Investigator); a copy of the IRB-approved consent form containing permission for audit by representatives of Sponsor, the IRB, and the FDA/health authorities; financial disclosure forms for all investigators listed on Form FDA 1572; site qualification reports, where applicable; verification of Principal Investigator acceptability from local and/or national debarment list(s).

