### 10.6.3 Clinical Laboratory Tests

Analysis Set: Safety

Laboratory data will be presented per cycle for each phase.

Baseline will be defined in each phase of the study. The baseline measurement will be the last pre-treatment measurement taken on or before Cycle1 Day1 in respective phase. For Dose Escalation phase, the baseline will be the last pre-treatment measurement taken on or before the Cycle 1 Day 1 dose for Romidepsin, and for Dose Expansion phase, the baseline will be the last pre-treatment measurement taken on or before Cycle 1 Day 1 dose of Romidepsin or Tenalisib whichever is earlier.

Absolute values of laboratory parameters will be presented at each visit using descriptive statistics (n, mean, median, standard deviation, minimum and maximum values).

The laboratory data will also be listed.

A separate listing of patients with abnormal laboratory test values will also be presented.

Hematology	Chemistry Panel I	Chemistry Panel II	Urinalysis	Other
Hematocrit	Total bilirubin	Blood glucose	Blood	PT
Hemoglobin	Alkaline phosphatase (ALP)	Urea or blood urea nitrogen	Glucose	INR
CBC with differentials	Alanine aminotransferase (ALT)	Albumin	Protein	
Platelet count	Aspartate aminotransferase (AST)	Total protein	Specific gravity	
WBC (Total and differentials)	Lactate dehydrogenase (LDH)	Total Cholesterol	Microscopic exam	
Red blood cell count	Gamma-glutamyl transferase	Triglyceride (TG)		
Absolute neutrophil count	Sodium	LDL		
Absolute lymphocyte count	Potassium	HDL		
	Calcium	TSH		
	Phosphorous	T3 (Total or Free)		
	Bicarbonate or Carbon Dioxide (CO2)	T4 (free)		
	Chloride	Creatinine		
	Magnesium			

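### SAP 10.6.3 summarises laboratory data only as absolute values by visit, from local laboratories at about 15 centres, so these tables cannot be read against the protocol's ULN-based AST/ALT, bilirubin and creatinine limits

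*SAP*

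**What the plan says.** The protocol synopsis gives "Approximately about 15 study centers". On where tests are run, Protocol 6.4 says: "The investigations will be performed at each local laboratory". Protocol 11.3 requires each site to file "a copy of the normal ranges for tests to be performed by that laboratory" before the trial starts.

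The protocol's limits for four tests use the ULN. Inclusion criterion 9 (Protocol 4.1) limits AST/ALT to 3 times ULN, or 5 times with liver involvement, and total bilirubin to 1.5 times ULN, or 3 times with Gilbert syndrome. Table 8 (Protocol 7.7.2) sets ALT/AST bands from above 1 times ULN upwards and bilirubin bands from above 1.5 times ULN upwards. It sets a creatinine threshold at 3 times baseline or 3 times ULN.

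For analysis, SAP 10.6.3 says: "Absolute values of laboratory parameters will be presented at each visit using descriptive statistics". The statistics are n, mean, median, SD, minimum and maximum. The section also plans a full listing and a listing of patients with abnormal values. It defines a baseline but plans no change from baseline, multiple of ULN, CTCAE grade or shift table, and it gives no rule on units. Protocol 9.4.2, by contrast, plans a tabulation of each patient's worst CTCAE grade for selected laboratory measurements.

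**The concern.** Safety is the primary endpoint, and the liver is one of the organs the protocol singles out: "Monitoring of liver enzymes and levels of TSH, T3, and T4 in subjects receiving Tenalisib is recommended based on target organ toxicity". In the earlier T-cell lymphoma study (Protocol 1.1.2), AST/ALT elevation has the largest count among treatment-related Grade 3 or higher toxicities: n=12, with 58 patients treated. The text does not say whether 12 counts patients or events.

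A reader of the study report will want to know how far patients moved towards the protocol's limits, and when. The by-visit table in SAP 10.6.3 is the only planned summary that follows laboratory values over time. On raw values pooled across laboratories it cannot answer that question, and in small columns a difference between visits or cohorts may partly reflect which laboratories contributed.

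**Working it through.** The plan states no figure to reproduce on this point. The check compares passages, with arithmetic only to show scale.

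**1. How many laboratories feed one column.** The planned maximum is 18 patients in escalation (unless dose levels are added) and 24 in expansion: 18 + 24 = 42. Over about 15 centres that is 42/15 = 2.8 patients per centre on average. An escalation cohort column holds 3 to 6 patients and an expansion group column 12, so a column may draw on several laboratories.

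**2. What a raw value means against a ULN limit.** Multiple = value / local ULN. The documents give no local ULNs, so assume ALT ULNs of 35 to 60 U/L.

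| Assumed ALT ULN (U/L) | 3 x ULN | 5 x ULN | 180 U/L as multiple of ULN |
|---|---|---|---|
| 35 | 105 | 175 | 180/35 = 5.1 |
| 40 | 120 | 200 | 180/40 = 4.5 |
| 50 | 150 | 250 | 180/50 = 3.6 |
| 60 | 180 | 300 | 180/60 = 3.0 |

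The same result is above 5 times ULN at the first laboratory, between 3 and 5 times at the next two, and exactly at 3 times at the last. Take two patients, both at 180 U/L, one at the first laboratory and one at the last. The SAP table would show mean 180, minimum 180, maximum 180 and SD 0, although the two are at 5.1 and 3.0 times ULN. If all local ULNs were equal the problem would vanish, but nothing in the documents says they are.

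**3. What the adverse event tables recover.**
- SAP 10.6.2 tabulates treatment-emergent adverse events by maximum CTCAE grade.
- Protocol 7.4.3 sends Grade 3 or 4 laboratory abnormalities to the adverse event page, but Grade 1 or 2 values only if clinically significant. Isolated abnormalities without clinical significance are left out if the investigator confirms this.
- Table 8 acts from ALT/AST above 1 times ULN. Its lowest band can therefore be missing from the adverse event tables.
- Under Protocol 7.4.2 a persistent event is recorded once, at its highest grade, so these tables do not show the course by visit.

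**4. What was dropped.** Protocol 9.4.2 plans worst grades for selected laboratory measurements as well as for adverse events. SAP 10.6.2 carries over the adverse event part. SAP 10.6.3 does not carry over the laboratory part and gives no reason. SAP Section 2 allows the SAP to modify protocol plans, so this is an unexplained omission and not a breach.

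**5. Paired analytes, a minor point.** The SAP test table has one line for "Urea or blood urea nitrogen" and one for T3, whether total or free. Protocol Table 4, footnote a, allows either form of the first: "Blood Urea Nitrogen is preferred; if not available Urea may be tested". By molecular weight, urea is 60.06/28.01 = 2.14 times BUN in the same mass unit. Total and free T3 are different quantities, and no unit conversion turns one into the other. The SAP has no rule for keeping the forms apart.

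**The case against.** The strongest reply is that ULN-scaled toxicity is already reported. Table 8 expresses transaminase and bilirubin grades as ULN multiples, so a table by CTCAE grade is a ULN-scaled table, and SAP 10.6.2 supplies one, overall and by suspected drug. The full and abnormal-value listings add patient-level detail. Eligibility and dose rules are applied to individual patients against their own laboratory's range, so no decision uses a pooled mean. Safety analysis is descriptive only.

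Much of this stands. Higher-grade hepatic toxicity will largely be visible, and patient management is untouched. What remains is the lower bands, the course over time, and the missing worst-grade laboratory table. The abnormal-value listing does not fill these gaps: it is not summarised, and SAP 10.6.3 does not define abnormal.

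A reader might go further and infer that the thyroid tables also fail against ULN limits. The documents do not support this: Protocol 3.4.5.1 recommends monitoring TSH, T3 and T4, but no ULN-based thyroid limit is set. Urea/BUN is neither a liver nor a thyroid test.

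A reader might also infer that the SAP will average total with free T3, or urea with BUN. The SAP does not say so. Its table follows the protocol's list of tests, and the same list puts the blood count with differentials on one line, which cannot be one averaged variable. Analysts would probably separate the forms. The study-specific Laboratory Manual, which is not among these documents, may deal with units.

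**Conclusion.** The point holds for ALT, AST, total bilirubin and creatinine. The by-visit tables in SAP 10.6.3 cannot be read against the protocol's ULN-based limits, adverse event tables cover this only in part, and the worst-grade laboratory tabulation in Protocol 9.4.2 is not carried over. For creatinine, Table 8 also allows a multiple of baseline, which the planned tables do not show either.

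The size is moderate and concerns how informative the safety tables are. DLT counts, MTD decisions and adverse event grade tables do not change. The conclusion rests on local reference limits differing between sites. The 35 to 60 U/L range is illustrative, and the true spread could be narrower or wider. The handling of T3 and of urea/BUN is a matter for clarification, not an established error.

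**What to change.** In SAP 10.6.3:

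- Add by-visit summaries of ALT, AST, total bilirubin and creatinine as multiples of the local laboratory's ULN in effect at the sample date. Keep raw values in the listing.
- Add the worst CTCAE grade per patient, as Protocol 9.4.2 foresees, with a baseline-to-worst shift table. This is needed alongside the first item because a mean multiple of ULN does not count the patients beyond a limit.
- As a minor clarification, report total T3 and free T3 separately, and express urea and BUN as one quantity in one unit.

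The cost is SAP wording, derived variables for the four tests, and two further tables. The normal ranges must already be supplied under Protocol 11.3. The ongoing burden is keeping each laboratory's ranges, with their effective dates, current in the database.

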#### 10.6.4 Physical Examinations

Analysis Set: Safety

Physical examination data will be listed for Screening visit in each phase of the study.

A separate listing of patients with abnormal findings will also be presented.

### 10.6.5 Vital Signs

#### Analysis Set: Safety

Vital signs will include pulse rate, respiratory rate, blood pressure, and temperature (oral/axillary). Weight will also be included here.

Baseline will be defined in each phase of the study. The baseline measurement will be the last pre-treatment measurement taken on or before Cycle1 Day1 in respective phase. For Dose Escalation phase, the baseline will be the last pre-treatment measurement taken on or before the Cycle 1 Day 1 dose for Romidepsin, and for Dose Expansion phase, the baseline will be the last pre-treatment measurement taken on or before Cycle 1 Day 1 dose of Romidepsin or Tenalisib whichever is earlier.

Absolute values of Vital Signs data will be summarized descriptively (n, mean, median, standard deviation, minimum and maximum) per cycle for every scheduled timepoint. A listing will also be provided.

A separate listing of patients with abnormal vital signs findings will also be presented.

### 10.6.6 Electrocardiogram

#### Analysis Set: Safety

- Baseline will be defined in each phase of the study. The baseline measurement will be the last pre-treatment measurement taken on or before Cycle1 Day1 in respective phase. For Dose Escalation phase, the baseline will be the last pre-treatment measurement taken on or before the Cycle 1 Day 1 dose for Romidepsin, and for Dose Expansion phase, the baseline will be the last pre-treatment measurement taken on or before Cycle 1 Day 1 dose of Romidepsin or Tenalisib whichever is earlier.
- Absolute values of ECG parameters [PR Interval, HR (heart rate), QT interval, QTcF (QT interval with Fridericia's correction), QRS Duration] as collected on CRF will be presented through n, mean, median, standard deviation, minimum, and maximum per cycle for every scheduled timepoint.
- A summary of abnormal ECG results will also be provided per cycle in each phase including baseline visit using frequencies and percentages.
- A listing of this data will also be provided.
- A separate listing for the abnormal ECG values will also be presented.

### 10.6.7 ECOG

#### Analysis Set: Safety

Baseline will be defined in each phase of the study. The baseline measurement will be the last pre-treatment measurement taken on or before Cycle1 Day1 in respective phase. For Dose Escalation phase, the baseline will be the last pre-treatment measurement taken on or before the Cycle 1 Day 1 dose for Romidepsin, and for Dose Expansion phase, the baseline will be the last pre-treatment measurement taken on or before Cycle 1 Day 1 dose of Romidepsin or Tenalisib whichever is earlier.

ECOG performance status (0=Normal activity, 1=Symptoms, but ambulatory, 2=In bed < 50% of the time, 3 and above=In bed > 50% of the time or 100% bedridden or are Dead), as reported in the eCRF, will be summarized per cycle in each phase with number and percentage for each status category. This data will also be listed.

## 11. Pharmacokinetic (PK) Analysis

PK analysis is not applicable for this SAP. The same will be prepared by a Clinical pharmacology Clinical Research Organization appointed by Rhizen and the analysis results will be shared for inclusion in the study report.

## 12. Exploratory analysis

*The analyses of correlative markers are exploratory and will not be used to guide treatment decisions.*

This is not applicable for this SAP. The same will be prepared by Rhizen and the analysis results will be shared for inclusion in the study report.

## 13. Protocol Deviations

Analysis set: Safety

A full list of protocol deviations for the study report will be compiled prior to database lock. All deviations will be reviewed by the Medical monitor prior to database lock. Each deviation will be categorized as major and minor and a decision will be taken by the medical monitor whether to include the subject in a PP analysis population set.

Protocol deviations will be presented as number and percentage of patients with minor and major deviations in the study. This data will also be listed as appropriate.

## 14. Listings

In addition to all the listings mentioned above, separate listings will be presented for the following:

- Screened patients
- Patients Eligibility
- Patient visits
- Study completion/Reasons for discontinuation/withdrawal of patient from the study
- Analysis populations
- Cancer Diagnosis
- Prior therapy
- mSWAT assessment
- Serology Assessment
- Study drug exposure
- Study drug accountability
- Target lesion assessment
- Non-target lesion assessment

- Disease Response assessment
- Overall tumor assessment
- Pregnancy test
- Investigator's Comments

